8.1.1.1. Lesions: Identification and Follow-up

Measurable Lesions

Measurable tumor lesions are defined as tumor lesions with an LD (measured in at least 1 dimension) with a minimum size as follows ([Eisenhauer 2009](#)):

- 10 mm by CT or MRI (with a scan slice thickness of no greater than 5 mm)

Measurable lymph nodes must be ≥ 15 mm on the short axis by CT or MRI (with a scan slice thickness of no greater than 5 mm); only the short axis is to be measured at baseline and follow-up.

Lytic bone lesions or mixed lytic-blastic lesions with a soft tissue component meeting the definition of measurability above can be considered measurable lesions.

Cystic lesions representing cystic metastases that meet the definition of measurability described above can be considered measurable lesions. If present, noncystic lesions should be selected as target lesions for this study.

A tumor lesion that has been previously irradiated may be considered measurable if unequivocal growth of the lesion has been demonstrated.

Target lesions: At baseline, up to 5 measurable tumor lesions/lymph nodes (with a maximum of 2 lesions per organ) should be identified as target lesions that will be followed to quantitate the status of disease during the study. Lesions with the LD, that are representative of all involved organs, and for which reproducible repeated measurements can be obtained should be selected as the target lesions.

At Screening and at each follow-up timepoint ([Table 1](#)), each target lesion should be measured and the overall tumor burden will be calculated as the sum of the diameters of the target lesions (LD for tumor lesions and short axis for lymph nodes) and documented in the eCRF. If a target lesion fragments into multiple smaller lesions, the LDs of all fragmented portions are added to the sum of the diameters. If multiple lesions coalesce, the LD of the coalesced lesion will be included in the sum of the diameters.

Nonmeasurable Lesions

Nonmeasurable lesions include tumor lesions with an LD < 10 mm, lymph nodes with ≥ 10 to < 15 mm short axis, or nonmeasurable lesions such as leptomeningeal disease, ascites, pleural or pericardial effusion, inflammatory breast disease, lymphangitic involvement of skin or lung, or abdominal masses/abdominal organomegaly identified by physical exam that is not measurable by CT scan or MRI ([Eisenhauer 2009](#)).

Nontarget lesions: All other lesions (or sites of disease) identified at baseline should be identified as nontarget lesions and recorded in the eCRF. Measurements of these lesions are not required, but the presence, absence, or unequivocal progression of each nontarget lesion should be recorded in the eCRF at each follow-up timepoint. Multiple nontarget lesions in the same organ may be noted as a single item on the eCRF.

New Lesions

Any new lesions should be identified and recorded at each follow-up assessment, as these are markers of disease progression. As defined in the RECIST v1.1 Guidelines ([Eisenhauer 2009](#)), new lesions include the following:

- A lesion in an anatomical location that was not scanned at baseline
- Equivocal new lesion of small size that with continued therapy and follow-up is found to progress and represent new disease (progression should be considered as of the date of the initial scan)
- Negative PET with FDG-PET at baseline, but has a positive FDG-PET at follow-up

No FDG-PET at baseline and a positive FDG-PET at follow-up that corresponds to a new site of disease as confirmed by CT (date of disease progression should be the date of the initial abnormal FDG-PET scan).

The need to initiate or increase the dose of a bisphosphonate and/or denosumab during the study **will be considered as indicative of clinical disease progression** leading to the discontinuation of participant from the active treatment phase **unless** disease progression can be completely ruled out and the exact reason for the use of these therapies is clearly documented in the participant's source documentation. All such cases must be first discussed with the Medical Monitor.

Note: Findings attributable to differences in scanning technique or a change in type of imaging (CT versus MRI) and findings representing something other than tumor (eg, healing or flare of existing bone lesions, necrosis of a liver lesion) should not be considered new lesions.

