- f. Predose and postdose blood samples for lerociclib concentration measurement are to be collected prior to and following the dose of lerociclib on Day 1 and Day 15 of Cycle 1, and on Day 1 of Cycles 2, 3, 4, and 5. The postdose blood sample can be collected between 2 hours and 6 hours (\pm 10 minutes) after the administration of lerociclib. It is important to record the actual time of collection. If the participant is due for a 2- or 6-hour 12-lead ECG assessment, the PK sample may be drawn at the same timepoint but should be obtained after the ECG.
- g. Radionuclide bone scans shall be performed at Screening for all participants every 8 weeks (\pm 7 days) for the first 12 months and every 12 weeks thereafter if initial bone scan is positive for bony lesion. If initial bone scan is negative for bony lesion, bone scan should be done annually or as clinically indicated per Investigator standard of care. All participants with a CR must have a radionuclide bone scan as part of confirmation of the CR. Additional bone scans may be obtained at the discretion of the Investigator, if clinically indicated. Participants with bone-only disease may be followed only with bone scans at the discretion of the Investigator. If CT or bone scan have been done for regular clinical care within 28 days before receiving the first dose of lerociclib, these may be used as baseline scans.
- h. Subsequent cycles may be postponed up to 14 days due to lerociclib interruption. Note that subsequent cycles should start on the original schedule (ie first dosing date).
- i. Participants in the 1L and 2L populations will receive the Investigator's choice of letrozole 2.5 mg daily or fulvestrant 500 mg (dosed according to schedule specified in the protocol).

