8.1.1. Antitumor Activity Assessments

For tumor assessment, all sites of disease, including but not limited to the chest, abdomen, and pelvis, should be assessed radiologically by CT or MRI at Screening and every 8 weeks for the first 12 months, then every 12 weeks until the occurrence of disease progression ([Table 1](#)). A central imaging vendor will be used to collect and hold these images for possible future review by independent radiologists. Objective response data collected for the clinical study report will be based on Investigator assessment.

Scans (CT or MRI) obtained prior to informed consent will not need to be repeated if performed within 28 days prior to dosing. Radionuclide bone scans shall be performed at Screening for all participants and annually thereafter or as clinically indicated. All participants with a CR must have a radionuclide bone scan as part of confirmation of the CR. Additional scans may be obtained at the discretion of the Investigator, if clinically indicated.

Participants with bone-only disease will be followed with bone scans only at Screening and every 12 weeks on treatment.

If a participant shows a radiological response (CR or PR), a confirmatory radiological assessment will be performed at least 4 weeks after the response was first noted. Participants who have a confirmed CR will have a bone scan to confirm absence of bony metastases.

For all participants (1L or 2L populations), if they remain on therapy for 12 months following enrollment, the timing of CT or MRI scans should be lengthened to every 12 weeks.

The same method of assessment (CT or MRI) should be used to characterize tumors at Screening and at all follow-up assessments. If PET is used, it should also be accompanied by spiral CT or MRI.

Investigators should follow RECIST v1.1 Guidelines ([Eisenhauer 2009](#)) for tumor assessments and determination of overall response.

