9.2. Analysis Sets

The following analysis populations will be used for presentation and analysis of data.

- Safety Analysis Set is defined as all enrolled participants who have received at least 1 dose of study intervention (NIMP or IMP).
- Full Analysis Set is defined as all enrolled participants who were exposed to lerociclib during the study.
- Response Evaluable Analysis Set is defined as all enrolled participants who were exposed to lerociclib during the study and who had measurable disease at baseline.

All safety analyses will be assessed using the Safety Analysis Set. Tumor response endpoints will be assessed using the Response Evaluable Analysis Set. Progression-free survival, OS, and QoL will be assessed using the FAS.

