4.10.3.2 Progression-free Survival (PFS)

Progression-Free Survival (PFS) is defined as the time to PFS event from first exposure to lerociclib. PFS event is defined as PD (per RECIST v1.1 as assessed by the investigator) or death due to any cause, whichever comes first. For participants without death or disease progression, PFS will be censored at the date of the last valid RECIST assessment unless otherwise stated. PFS duration will be calculated as

$$\text{Date of observation} - \text{Date of first exposure to lerociclib} + 1$$

where date of observation is the earliest of death, progression, or censoring.

PFS events and censoring rules, such as initiation of disallowed anticancer therapy, are defined below in Table 2.

All valid RECIST assessments after start of treatment will be used in the PFS analysis regardless of whether they were collected as part of scheduled or unscheduled visits. RECIST assessments based on scans performed after the end of lerociclib therapy will be used in the analysis of PFS if prior censoring events have not been observed.

Table 2 Censoring Rules for Progression-Free Survival

| Situation | Outcome | Date of Event/ Censoring |
|--|---------|---|
| PD or death, whichever occurred first, before exposure to subsequent antineoplastic therapy, withdrawal of consent, loss to follow up, data cutoff, or end of study. | Event | Earliest date of documented progression or death |
| No baseline disease assessment | Censor | Date of first exposure |
| No valid post-baseline tumor assessment | Censor | Date of first exposure |
| PD or death immediately after missing ≥ 2 consecutive scheduled tumor assessment | Censor | Date of last valid tumor assessment prior to the missing tumor assessments |
| No PD or death on or before 
 Database cut End of study Start of new antineoplastic therapy | Censor | Date of last tumor assessment on or prior to earliest censoring event listed in first column of this row. |

Descriptive summaries of time to event data will include median, twenty-fifth and seventy-fifth percentiles, and associated 2-sided 95% CIs based on Kaplan-Meier methods. Survival estimates along with corresponding 95% CIs using the log-log transformation will be provided at certain intervals as data allows.

A Kaplan-Meier plot will be presented and will include the number of participants at risk over time by line of therapy. No formal statistical hypothesis will be tested.

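### The imaging rules do not say whether a bone-only participant with a CT/MRI-measurable bone lesion keeps CT/MRI follow-up; if followed by bone scan alone, that participant counts against ORR and CBR without being assessable for either.

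*Protocol*

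**What the plan says.** **Measurability.** Protocol 8.1.1.1 defines measurable lesions by size on CT or MRI and adds: "Lytic bone lesions or mixed lytic-blastic lesions with a soft tissue component meeting the definition of measurability above can be considered measurable lesions". The same section requires that, at Screening and each follow-up timepoint, "each target lesion should be measured and the overall tumor burden will be calculated as the sum of the diameters of the target lesions". It also says that lesions "for which reproducible repeated measurements can be obtained should be selected as the target lesions".

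**Imaging.** Four places bear on a bone-only participant:

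- Protocol 8.1.1, general rule: all sites of disease "should be assessed radiologically by CT or MRI at Screening and every 8 weeks for the first 12 months", and less often after that.
- Protocol 8.1.1, later in the section: "Participants with bone-only disease will be followed with bone scans only at Screening and every 12 weeks on treatment".
- Protocol 1.3, Schedule of Activities footnote g: "Participants with bone-only disease may be followed only with bone scans at the discretion of the Investigator".
- SAP Appendix 6.1: the same optional wording as footnote g.

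**Analysis set.** Protocol 9.2 and SAP 4.5 define the Response Evaluable set as enrolled participants "exposed to lerociclib during the study and who had measurable disease at baseline". No post-baseline scan is required and bone-only disease is not excluded. SAP 4.10.2 uses this set for ORR, CBR, DOR and TTR.

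**PFS.** SAP 4.10.3.2, Table 2, censors at the date of first exposure where there is "No valid post-baseline tumor assessment". It does not define a valid assessment.

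**The concern.** Entry to the response denominator depends on a CT/MRI measurement at baseline. The follow-up rule for bone-only disease can remove CT/MRI afterwards. A bone scan gives no lesion diameter, so the participant stays in the denominator while the measurement needed for a response is not taken.

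A site that follows the mandatory sentence in 8.1.1, or that uses the discretion in footnote g, is within the protocol and loses the response endpoint for that participant. A site that follows the general CT/MRI rule and the target-measurement rule is also within the protocol and keeps it. The same kind of participant can thus be handled differently from site to site.

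Any resulting error in ORR and CBR runs in one direction, downward, and more participants would not remove it. PFS could lose follow-up time from the same people.

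**Working it through.** **1. The plan's own precision figure.** Protocol 9.4 and SAP 4.12 assume at least 80% of 50 participants per line have measurable disease: 0.80 × 50 = 40. The widest exact (Clopper-Pearson) 95% interval at n = 40 is at 20/40, from 33.8% to 66.2%, a half width of (66.2 − 33.8)/2 = 16.2 points. The normal approximation gives 1.96 × √(0.25/40) = 15.5 points. The stated figure of about 16% is reproduced.

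**2. What happens without diameters.** Take a bone-only participant with a measurable soft-tissue component, CT/MRI at Screening and bone scans alone on treatment.

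- The participant is in the Response Evaluable set on baseline measurability. SAP 4.6 lists target lesions and measurable disease as separate baseline variables, so not choosing the lesion as a target does not take the participant out of the set.
- Protocol 8.1.1.2 assigns not evaluable where information is inadequate. In Protocol Table 7, a target that is not evaluable, with no nontarget progression and no new lesion, gives an overall response of not evaluable.
- SAP 4.10.2 reserves Non-CR/Non-PD for participants without measurable disease, so a stable bone scan cannot be recorded that way here.
- The on-treatment options are therefore not evaluable or progression. Neither counts toward ORR or CBR, and percentages use the full set as denominator (SAP 4.2.4).

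**3. Size for ORR.** Let p be the ORR among participants who are re-measured and b the number of the 40 followed in this way. Expected reported ORR = p × (40 − b)/40, a loss of p × b/40. Neither p nor b is in the documents; both are assumed below.

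| Assumed p | b = 1 | b = 2 | b = 4 |
|---|---|---|---|
| 30% | −0.75 | −1.5 | −3.0 |
| 40% | −1.0 | −2.0 | −4.0 |
| 50% | −1.25 | −2.5 | −5.0 |

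Entries are percentage points. The loss is linear in b, so the per-participant figure of 0.75 to 1.25 points is the one to carry forward.

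**4. PFS.** If a not-evaluable timepoint is not a valid assessment, a participant with only such timepoints and no progression falls under the Table 2 row for no valid post-baseline assessment and is censored at first exposure. If it is valid, censoring moves to the last scan. Table 2 supports either reading.

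**The case against.** The strongest reply is that the protocol already contains the rule that is needed. Section 8.1.1 calls for CT/MRI of all disease sites and for the same method at Screening and at follow-up. Section 8.1.1.1 requires each target to be measured every time and prefers targets that can be re-measured. Footnote g leaves bone-scan-only follow-up to the Investigator, who may keep CT/MRI. This stands. A reader might infer from the single sentence in 8.1.1 that these targets are never re-measured; the documents do not support that.

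The Schedule of Activities also has a tumor evaluation at end of treatment, and Protocol 7.1.1 asks for CT or MRI after discontinuation for reasons other than progression if none was done in the prior 4 weeks. One late scan could show stable disease or supply a valid PFS assessment. It cannot by itself give a confirmed response, which needs a second assessment at least 28 days later (SAP 4.10.2.1). Participants still on treatment at the primary analysis, about 6 months after the last participant's first dose, would not have it.

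The term bone-only disease is undefined. A lesion with a sizeable soft-tissue component might not be thought bone-only, and then the conflict disappears. Conversely, if bone scan alone applied at Screening too, measurability could not be established and the participant would not enter the set. However, the Schedule of Activities requires a Screening tumor evaluation without a bone-only exception, so baseline CT/MRI followed by bone scans is a plausible path.

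Finally, ORR is a secondary endpoint in a descriptive study with no hypothesis test, and the likely shift is small beside the planned interval. That limits the importance of the point but does not resolve the contradiction.

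**Conclusion.** The point holds as an unresolved contradiction with a possible downward bias in ORR and CBR. Each participant in the Response Evaluable set who is followed by bone scan alone lowers expected ORR by p/40: 0.75 to 1.25 points for an assumed true ORR of 30% to 50%, with 40 in the set. The planned half width is about 16 points, so the effect is modest unless several participants per line are affected. How many would be is not in the documents.

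A reader might go further and call these participants automatic non-responders, or say their PFS is censored on the first day of lerociclib. Both are possible outcomes, not certain ones. They depend on the Investigator's imaging choice, on any end-of-treatment scan, and on the undefined terms bone-only disease and valid assessment.

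**What to change.** - In Protocol 8.1.1, footnote g and SAP Appendix 6.1, reconcile the mandatory and optional wording with the target-measurement rule in 8.1.1.1.
- Define bone-only disease, for imaging purposes, as disease with no measurable (target) lesion. Bone-scan-only follow-up then applies to nobody in the Response Evaluable set, and participants with measurable disease stay on the existing CT/MRI schedule.
- In the SAP, state how a Response Evaluable participant with no post-baseline target measurement counts in ORR and CBR, and whether a not-evaluable timepoint is a valid assessment in Table 2.

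The bone-scan interval also differs between these passages and needs reconciling, but nothing above depends on it.

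The cost is a short definition, aligned wording in three places, and continued CT/MRI for a few participants on the schedule that already applies generally. That carries radiation exposure from CT, which Protocol 2.3.2 lists as a study-procedure risk. Removing such participants from the set instead would cost precision: the worst-case exact half width rises from 16.2 points at n = 40 to 16.6 at n = 38 and 17.1 at n = 36. Keeping CT/MRI leaves the set at 40 and removes this source of bias.

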8.1.1.2. Definitions of Tumor Response and Disease Progression

The determination of tumor response and progression will be based on the RECIST v1.1 criteria ([Eisenhauer 2009](#)). The definitions for tumor response per RECIST, v1.1 are provided below.

Evaluation of Target Lesion Response

- **Complete response:** Disappearance of all target lesions. Any pathological lymph nodes (whether target or nontarget) must have reduction in short axis to < 10 mm
- **Partial response:** At least a 30% decrease in the sum of diameters of target lesions, taking as reference the baseline sum of diameters
- **Progression of disease:** At least a 20% increase in the sum of diameters of target lesions, taking as reference the smallest sum on study (this includes the baseline sum if that is the smallest on study). In addition to the relative increase of 20%, the sum must also demonstrate an absolute increase of at least 5 mm. The appearance of 1 or more new lesions is also considered progression
- **Stable disease:** Neither sufficient shrinkage to qualify for PR nor sufficient increase to qualify for PD, taking as reference the smallest sum of diameters while on study

A response category of not evaluable is to be used when there is inadequate information to otherwise categorize the response status.

Evaluation of Nontarget Lesions

- **Complete response:** Disappearance of all nontarget lesions and normalization of tumor marker level. All lymph nodes must be < 10 mm short axis
- **Non-CR/Non-PD:** Persistence of 1 or more nontarget lesions and/or maintenance of tumor marker level above the normal limits
- **Progression of Disease:** Unequivocal progression of existing nontarget lesions or the appearance of at least 1 new lesion

Evaluation of Overall Response

[Table 7](#) describes the evaluation of overall response at each timepoint based on target and nontarget lesion responses at each timepoint, as well as the appearance of new lesions. The best overall response is the best response recorded from the start of the treatment until disease progression. Confirmation of CR and PR is required as previously described.

Table 7: Evaluation of Overall Response at Each Timepoint

| Target Lesions | Nontarget Lesions | New Lesions | Overall Response |
|----------------|-------------------|-------------|------------------|
| CR | CR | No | CR |
| CR | Non-CR/Non-PD | No | PR |
| CR | Not evaluated | No | PR |

Table 7: Evaluation of Overall Response at Each Timepoint (Continued)

| Target Lesions | Nontarget Lesions | New Lesions | Overall Response |
|----------------|--------------------------|-------------|------------------|
| PR | Non-PD/not all evaluated | No | PR |
| SD | Non-PD/not all evaluated | No | SD |
| NE | Non-PD | No | NE |
| PD | Any | Yes or No | PD |
| Any | PD | Yes or No | PD |
| Any | Any | Yes | PD |

CR = complete response; NE = not evaluable; PD = progressive disease; PR = partial response; SD = stable disease.
Source: [Eisenhauer 2009](#)

8.1.2. Patient-reported Outcomes

Patient-reported outcomes will be assessed in all participants as indicated in the SoA ([Table 1](#)) using the following PRO measures: the EORTC questionnaire developed to assess the QoL of cancer patients (EORTC-QLQ-C30), the EORTC questionnaire for assessing QoL in breast cancer patients (EORTC-QLQ-BR23), the EQ-5D-5L questionnaire, and the FACIT item GP 5 (“I am bothered by side effects of treatment”) rated on a 5-point Likert scale. Please refer to [Appendix 5](#) for samples of these 4 questionnaires.

Questionnaires and instructions will be provided electronically.

When possible, the questionnaires are to be completed in the same order at each visit and should be completed before any other procedures are performed.

If the participant is unable to complete the questionnaire during one of the scheduled visits, then the reason for not completing the questionnaire should be documented.

